### 11.6.3 Exploratory Analyses

This study offers the opportunity to explore several important questions related to the delivery and the efficacy of HIV prevention intervention for women. We will explore characteristics of site related to the delivery and potential effect on effectiveness. Site characteristics that will be studied include: individual clinic; MMTP versus drug-free outpatient treatment program; and Node. Hierarchical models (Bryk and Raudenbush, 1992), a special case of MEMs, will be used to study these characteristics. In addition, in an exploratory fashion we will study the effect of individual characteristics, by including these factors in the models described above. Factors to be studied especially include: (1) putative mediators, especially perceived self-efficacy variables and the observable skills variables; and (2) putative moderators, especially frequency of drug use, proportion of drugs or alcohol with sex occasions of all sexual occasions, extent of abuse, extent of perceived barriers to safer sex (especially fear of partner abuse) and monogamy status.

### 11.7 Analysis of Safety Measures

For each individual adverse experience, each participant will be categorized by the maximal severity reported during the intervention phase. Adverse experiences occurring during screening but ending prior to randomization, or those starting during screening and continuing into the randomization phase with the same or less severity will be excluded. The severity categories are: none (if the participant never had the adverse experience), mild, moderate, severe, life threatening and lethal. If a participant has an adverse experience more than once, then the adverse effect with most severe rating will be used in the analysis. It may be necessary to group the individual adverse experiences before any analysis can be performed. If this is necessary, then the coding will be performed centrally by Long Island node personnel.

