**TABLE 1: STUDY FLOW CHART**

Protocol Number 0019						
Study Activity	Visit 0	Visit 1	TX Session 1-5 a	Visit 2	Visit 3	Visit 4
	Day #	Day #	Day #			
Consent for screening assessment	1					
Screening assessment	1					
Obtain written informed consent	1					
Conduct baseline assessment		1-30				
Randomization of cohort			When 3 participants (but no more than 8) are in the cohort			
Attend intervention session(s)			Start approx day 8-36, attend over 1 or 3 weeks			
Conduct post intervention assessment				21 days after 1 st treatment session		
Conduct 3 mo. Follow up assessment					15 weeks after 1 st treatment session	
Conduct 6 mo. Follow up assessment						27 weeks after 1 st treatment session

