## **6.3 Administration of Study Therapies**

The SSB intervention will be delivered in 5-1 ½ hour group sessions, on a twice-weekly basis, over a consecutive 3-week period. The HE intervention will be delivered in 1 hour group session.

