### **8.5 Adverse Event Evaluation**

An adverse event (AE) is defined as any reaction, side effect or untoward event that occurs during the course of the clinical trial. The possibility of abusive partner behavior and/or a marked increase in emotional distress (defined as an increase in depression and/or anxiety symptoms) are the foreseeable adverse effects of participation. Possible triggers for these effects could be: introduction of (male or female) condoms or other methods of protection; introduction of safer sex negotiation; refusal of unprotected sex; or partner knowledge of the woman's participation in a woman's intervention. Subjects are advised to observe any signs of anger in their partners, and any of these problems in themselves, and to discuss this with study staff immediately. Study staff will be trained to provide crisis intervention and referral for clinical emergency situations. In addition, all study assessments contain modules concerning abuse that can alert study staff to evolving risk. The occurrence of AEs will be determined through the use of an AE Worksheet (consisting of one general AE question and a follow up question to gather more information) filled out by the RA at baseline, immediate post treatment, 3 and 6 month follow up assessments. All SAEs will be recorded, respectively, on the AE Case Report Form (CRF) and SAE Form and SAE Summary Report. The procedures for detecting, reporting and monitoring SAEs are described in section 9.0.

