All study related AEs and SAEs will be followed until resolution. Monitoring and reporting of SAEs will be maintained by the: CTP staff members (e.g. research assistants, therapists, etc.); CTP Site Coordinator; Protocol PI; Study Project Manager; Lead Investigator; and NIDA Medical Monitor.

Figure 3 presents a flow chart for AE and SAE reporting. Only SAEs and related AEs will be recorded and entered into the study database (via the AE CRF). All SAEs will be recorded on the AE CRF, the SAE Form, and a summary narrative provided via the SAE Summary Report. The AE CRF is a form that will be used to document any adverse event that is thought to be serious or study related. The AE CRF is completed at each assessment point and on an as needed basis. If the adverse event is found to be serious, then a SAE Form and SAE Summary Report must be completed. The SAE Form should be completed by or in consultation with the Study Clinician. The SAE Summary Report contains demographic information and an event narrative and should be completed by the Study Clinician.

All SAEs must be reported by fax of the AE CRF, within 24 hours to the Lead Investigator, Protocol PI, Node PI, NIDA Medical Monitor, and to IRBs in accordance with their guidelines. The Study Clinician will be responsible for reviewing the AE CRF and SAE Form, querying the staff as needed, and completing an SAE Summary Report, to be co-signed by the Lead Investigator. Within 14 days, the AE CRF and the SAE Form and the signed SAE Case Summary are forwarded to the NIDA Medical Monitor, Protocol PI, and Node PI. At the same time, reports will be submitted to all involved IRBs per reporting requirements.

All study staff – including research assistants, therapists, CTP Site Coordinator, Protocol PI, Lead Investigator, and Study Project Manager, will receive common training for AE and SAE detection, monitoring and reporting. Training will include: definition of AEs; definition and grading of SAEs; indications and procedures for completing the AE log; indications and procedures for completing AE CRFs; indications and procedures for completing SAE Forms and SAE Summary Reports; and procedures for reporting SAEs.

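### Section 11.7 confines the adverse event severity analysis to an undefined intervention phase, most naturally ending at day 21, although adverse events are elicited up to 6 months

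*Protocol*

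**What the plan says.** Section 11.7 fixes the period of the safety analysis: "each participant will be categorized by the maximal severity reported during the intervention phase". It sets aside screening events that end before randomization, and those "continuing into the randomization phase with the same or less severity will be excluded". Neither the intervention phase nor the randomization phase is defined in the protocol.

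Collection runs longer. Under Section 8.5 the AE Worksheet is "filled out by the RA at baseline, immediate post treatment, 3 and 6 month follow up assessments", and Section 9.1.2 and Table 2 agree. Table 1 puts Visit 2 at 21 days, Visit 3 at 15 weeks and Visit 4 at 27 weeks after the first session, with one schedule for both arms.

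Delivery differs by arm. Section 6.3 gives SSB "on a twice-weekly basis, over a consecutive 3-week period", and for the comparator: "The HE intervention will be delivered in 1 hour group session". Table 1 has participants "attend over 1 or 3 weeks".

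Sections 8.5 and 9.1.1 name abusive partner behavior and a marked rise in emotional distress as the foreseeable harms. The triggers listed in Section 8.5 include bringing in condoms, negotiating safer sex, refusing unprotected sex, and the partner learning that the woman is taking part.

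**The concern.** The listed triggers arise in the woman's relationship, and nothing ties them to the weeks in which sessions are held. The primary hypothesis in Section 3.1 looks for behavior change at 3 and 6 months. If SSB changes behavior as intended, negotiation and refusal will continue well past day 21, and so will the opportunity for the harms that the protocol expects from them. An analysis that stops at day 21 could show little in either arm while the later reports sit in the database untabulated.

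This is more than detail left to an analysis plan. The protocol states a restriction, and it fits badly with the protocol's own collection schedule.

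**Working it through.** **1. Where the phase most naturally ends.** Three features of the protocol point to Visit 2:
- Sections 4.0 and 8.0 label the later visits three and six months post-intervention.
- Table 2 places the treatment termination form at Visit 2 and the follow-up termination form at Visit 4.
- Visit 2 is named the immediate post-intervention visit.

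Against this, 11.7 contrasts the phase only with screening, and it codes a participant as having no event only if she never had it. That wording could also fit all time after randomization. The text does not settle the matter.

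**2. Share of follow-up covered if the phase ends at Visit 2.** Inputs are from Table 1, counted from the first session.
- Follow-up: 27 × 7 = 189 days.
- Covered: 21 / 189 = 11%.
- Left out: 189 − 21 = 168 days, and 168 / 189 = 89%.

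Section 4.0 counts Visit 2 as on time up to 14 days late, and the 6-month visit as on time up to 14 days early. The largest on-time share is therefore (21 + 14) / (189 − 14) = 35 / 175 = 20%. These figures are the same in both arms.

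**3. Sizing in events.** The protocol gives no adverse event rate. I assume a constant hazard, 240 women per arm (Section 4.0) and a 27-week risk P of 5%, 10% or 20%. The expected number of women with an event by day d is 240 × [1 − (1 − P)^(d/189)].

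| Assumed P | By day 21 | By day 189 |
|---|---|---|
| 5% | 1.4 | 12 |
| 10% | 2.8 | 24 |
| 20% | 5.9 | 48 |

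**4. The delivery-time reading.** If the phase meant the time over which sessions are delivered, SSB would have 21 days. HE would have 7 days (Table 1) or 1 day (Section 6.3), giving ratios of 21 / 7 = 3 and 21 / 1 = 21. At P = 10% and equal hazards, the expected counts are 2.8 for SSB against 0.9 or 0.1 for HE. For P from 5% to 20%, the ranges are 1.4 to 5.9 for SSB, and 0.5 to 2.0 (7 days) or 0.1 to 0.3 (1 day) for HE. SSB would look worse only because it was watched longer. These figures apply under this reading alone.

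**5. The abuse instrument.** Table 2 schedules it at baseline, 3 months and 6 months, not at Visit 2. Section 8.4.7 asks about frequency over the past 3 months, roughly 13 weeks. Visits at weeks 15 and 27 therefore look back over about weeks 2 to 15 and 14 to 27, which is almost exactly the period that a day-21 cut-off leaves out.

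**The case against.** **The phase may be wider than day 21.** On the broad reading in step 1 nothing is lost, and the defect is only an undefined term. That reading is possible. It requires visits labelled post-intervention to fall inside the intervention phase, so it is not the natural one.

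**Other safeguards exist.** Section 9.1.2 has the AE case report form completed at each assessment, and study-related events and SAEs followed to resolution. Section 9.1.4 gives the DSMB adverse event analyses with no phase limit. This stands: late harm is not lost from the trial. It does not repair the trial's own planned safety analysis.

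**A reader might infer that the arms are compared over unequal windows.** The documents do not support that as a fact. One session and three weeks are delivery times, not a definition of the phase. Under the delivery-time reading HE would have no scheduled AE Worksheet inside its phase, which is implausible for a planned analysis. Section 11.7 also describes how each participant is categorized and states no between-arm test.

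**A reader might also infer bias from the relatedness filter.** Non-serious events reach the database only if the study clinician judges them study-related, and the blinding effort in Section 6.3.2 mentions only the research assistants. But this is a data-capture rule in Section 9.1.2, not an error in 11.7, and SAEs are entered whatever their relatedness. Silence about the clinician's blinding does not show that attribution differs by arm.

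**Conclusion.** The point holds in a limited form. Section 11.7 ties the severity analysis to a term that the protocol does not define and that, on its most natural meaning, contradicts the purpose of eliciting adverse events to 6 months. If the phase ends at Visit 2, about 89% of scheduled follow-up (at least 80% allowing for on-time visit windows) falls outside the analysis in both arms, together with the 3- and 6-month reports. Under a constant hazard, the analysis would see roughly one event in eight or nine. That last figure rests on my assumed risks; the shares of time come from Table 1 and Section 4.0.

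Unequal windows by arm remain a conditional possibility, not a finding. The exclusion affects the 11.7 analysis only.

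**What to change.** In Section 11.7, replace the reference to the intervention phase with a window running from randomization through the 6-month follow-up assessment, the same in both arms. Use one term for post-randomization time throughout the section. This brings 11.7 into line with Sections 8.5 and 9.1.2 and Table 2. It costs a change of wording: the related events and SAEs from the later visits already enter the database.

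As a supporting analysis, compare the arms on the past-3-month physical, sexual and emotional abuse items at 3 and 6 months, adjusted for baseline. The data are already scheduled, so the cost is a little extra analysis.

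I do not recommend entering every AE Log item regardless of relatedness. That would reverse the database rule in Section 9.1.2 and require new form specifications and data dictionaries at each node (Sections 15.1 and 15.4). The window can be corrected without it.

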### 11.8 Interim Analysis

We propose an interim analysis of data of baseline and 3-month follow-up assessment of ½ of the study sample. We will use the method of stochastic curtailment, with conditional power analysis (Lan and Wittes, 1982; Lan and Wittes, 1988; Jennison and Turnbull, 1989), to examine the possibility of early stopping. Accordingly, our analyses will proceed from the following rationale: T will be the test statistics for testing the primary

null hypothesis for the primary outcome  $H_0: B_1 > 0$ .  $D(1)$  will be the interim analysis data. The examination of early stopping will be based on the conditional power analysis, whereby:  $P(0) = P(T \text{ will reject } H_0 \text{ at the end of the study} / D(1), B_1 = 0)$ . If  $1 - P(0) \geq 0.8$ , stopping will be recommended due to futility. If  $1 - P(0) < 0.8$ , continuation will be recommended.

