## **9.3 Trial Efficacy**

In view of the limited (i.e. single-study) evidence of the efficacy of this intervention, only within a methadone maintenance treatment program, we plan to conduct an interim analysis, primarily for futility. This plan is described in Section 11.8.

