### **11.2 Sample Size and Statistical Power**

The sample size is determined to ensure sufficient power (at least 80%) of a significance test (with level of significance  $\alpha=0.05$ ) to detect a clinically meaningful intervention effect with respect to the primary outcome measure (number of unprotected penetrative sex occasions).

The study design is a stratified cluster randomization trial (Donner and Klar, 2000). The intervention groups constitute the clusters. Each intervention group will consist of approximately 3 to 8 women depending on the number of eligible subjects recruited in the fixed time interval of 4 weeks. The strata are the 12 CTP sites – in which 40 participants per stratum will be enrolled. Thus, within each stratum, 5 to 10 clusters will be randomized in a balanced fashion to the two interventions. Below is presented the power of the test for comparison of the two interventions subject to these design and recruitment restrictions. Tables 1 and 2 were developed for different counts of CTPs (with the number of subjects per CTP fixed at 40). The two tables corresponding to 12 CTPs (and shown in the protocol) resulted in power values that were closest to our goals.

The power analysis for the stratified cluster randomization trial is based on a test statistic proposed by Liu & Liang (1997). The test statistic is based on generalized estimating equation (GEE). The power analysis takes into account the fact that data are correlated (repeated observations on a subject, the measurements of subjects belonging to the same intervention group (cluster) and from the same CTP (strata) and that the outcome follows a non-normal distribution.

The test statistic is actually a quasi-score statistic based on the generalized estimating equation. The asymptotic distributions of the test statistic under  $H_0$  and  $H_1$  are both known. In the analysis we assume the outcome (the number of unprotected sex occasions) follows a Poisson distribution with the marginal mean being a function of the intervention. In this case, under the null hypothesis the test statistic converges to Chi-square distribution with 1 degree of freedom. Under the  $H_1$ , the test statistic converges to non-central Chi-square distribution with 1 degree of freedom. After we specify the parameters in the linear predictor for the mean and in the covariance matrix of the outcome (that is, the working correlation matrix which does not have to be necessarily

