## **11.5 Analytic Plan**

### **11.5.1 Testing and estimation**

All testing will be two-sided and significance will be judged at level  $\alpha=0.05$ . Effects will be reported with point estimate and 95% confidence intervals in addition to p-values.

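### The futility rule in section 11.8 computes conditional power under no effect, so it recommends stopping unless SSB is already close to significance at the interim

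*Protocol*

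**What the plan says.** Protocol section 9.3 gives the purpose: "we plan to conduct an interim analysis, primarily for futility", and refers to section 11.8 for the plan. Section 9.1.4 describes the purpose in the same way and also defers to 11.8.

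Section 11.8 sets the timing: "We propose an interim analysis of data of baseline and 3-month follow-up assessment of ½ of the study sample". It names the method: "We will use the method of stochastic curtailment, with conditional power analysis". It then defines P(0) as the probability that the test statistic T will reject H0 at the end of the study, conditional on the interim data D(1) and on B1 = 0. If 1 − P(0) is 0.8 or more, "stopping will be recommended due to futility"; otherwise continuation is recommended. No conditional power under a planned effect or under the observed trend is mentioned. The null is written there as B1 > 0.

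Two other sections matter. Section 11.5.1 states "All testing will be two-sided and significance will be judged at level" α = 0.05. Section 11.2 sizes the trial for "sufficient power (at least 80%) of a significance test".

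**The concern.** In the primary model of section 11.6.1, β1 is the intervention coefficient, so B1 = 0 means no SSB effect. Conditional power at that value asks whether the trial would still reject if SSB had no effect in the data yet to come. That quantity supports stopping early because a positive result is nearly assured. Futility asks the opposite question: if SSB works as planned, is there still a reasonable chance of success? Section 11.8 uses the first quantity to answer the second question.

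A promising interim result would then be labelled futile, because little can be gained from future data that are assumed to show nothing. At stake are the chance of ending a trial of an effective intervention and the power claimed in section 11.2.

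**Working it through.** **Inputs.** Two-sided α = 0.05, c = 1.960 (section 11.5.1). Stop when P(0) ≤ 0.20 at B1 = 0, on half the sample (section 11.8); nominal information fraction t = 0.5. Means, correlations and layouts come from section 11.2.

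**1. Reproducing the protocol's power.** With two follow-up measures, m women per group and k groups per arm per site:

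Var(difference) = [μ_SSB/(12·k_SSB) + 17/(12·k_HE)] × {[(1+ρ1)/2 + (m−1)ρ2]/m − ρ3}, and power = Φ(δ/SE − 1.96).

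For Table 1 with ρ1 = 0.40, ρ2 = 0.10, ρ3 = 0.05 and 17 vs 16: (16+17)/60 = 0.55; (0.7+0.3)/4 − 0.05 = 0.20; variance 0.11; SE 0.332; δ/SE = 3.015; power 0.854, against 0.85 printed. All 72 entries without over-dispersion in Tables 1 and 2 reproduce within 2 points.

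**2. The rule as a bound on interim z.** Under zero drift, P(0) = 1 − Φ[(c − z√t)/√(1−t)]. Setting this to 0.20 gives

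z = (1.960 − 0.8416√(1−t))/√t.

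At t = 0.5: (1.960 − 0.595)/0.7071 = 1.93, two-sided p about 0.054. An interim z of 1.00 gives P(0) = 3.8%, and 1.645 gives 13.0%; both would be called futile. An interim z of 1.96 gives 20.8% and only just continues.

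**3. Operating characteristics at t = 0.5.** The drift is θ = 1.96 + z(power). P(stop) = Φ(1.93 − θ√0.5). Net power is P(interim z > 1.93 and final z > 1.96), from the bivariate normal with correlation √0.5.

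| Design power | Stopping recommended | Power if followed |
|---|---|---|
| 80% | 48% | 50% |
| 90% | 36% | 63% |
| 95% | 27% | 73% |
| 99% | 14% | 86% |

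With no effect, the rule recommends stopping 97% of the time.

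**4. Over the protocol's own grid.** Here θ = δ/SE from step 1, for all ρ values and both layouts. Over-dispersed cells multiply the variance by 1/(1 − ρ2 − ρ3), as section 11.2 states. That formula does not match the printed over-dispersed powers exactly: in four rows checked it differs by up to about 3 points, for example 0.769 against 0.80.

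| Means | Stopping recommended under the true effect (t = 0.5) | Net power |
|---|---|---|
| 17 vs 15 | 0.1–21% | 79–99.9% |
| 17 vs 15.5 | 4–46% | 52–96% |
| 17 vs 16 | 30–72% | 24–69% |

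**5. Information fraction.** If B1 is the effect pooled over both follow-ups, half the sample with 3-month data only gives

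t = 0.5 × {[(1+ρ1)/2 − ρ2]/m + ρ2 − ρ3} / {(1−ρ2)/m + ρ2 − ρ3}.

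The lowest value, at ρ1 = 0.4, ρ2 = ρ3 = 0.1, m = 4, is 0.5 × 0.6/0.9 = 0.33. The highest, at ρ1 = 0.8, ρ2 = 0.15, ρ3 = 0.05, m = 8, is 0.5 × 0.19375/0.20625 = 0.47. At t = 0.40 the bound rises to 2.07; an effect with 80% design power is then stopped 62% of the time, leaving 37% power.

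**The case against.** Several points on the other side are fair.

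- **The effects the protocol relies on are larger.** Section 11.2 claims sufficient power for 17 vs 15 and 17 vs 15.5, and calls power for 17 vs 16 limited. A reader might infer that an effective intervention would usually be stopped, or that 80% power cannot be delivered at all. The protocol's figures do not support either statement in general. For 17 vs 15, stopping is recommended at most 21% of the time at t = 0.5 and net power is 79% or more. Even at 80% design power the stopping rate is 48%, just under half.
- **The information fraction may be 0.5.** In section 11.6.1 time is coded 0 at 3 months. With the interaction kept, β1 is the 3-month effect, and half the sample supplies about half its information. The range 0.33–0.47 holds only if the interaction is dropped and β1 covers both visits, so it is an assumption and not a fact of the plan.
- **It is only a recommendation.** The data and safety monitoring board works under its own procedures and nothing makes the rule binding, so the trial does not stop automatically. It is still the only prespecified criterion the board is given.
- **H0 is written one-sided.** At one-sided 0.05 and t = 0.5 the bound is 1.485; an effect with 80% design power is stopped 39% of the time, leaving 57% power. The rule is milder, but the defect is the same.

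None of this removes the core error: no other section supplies a conditional power under a planned effect.

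**Conclusion.** The concern holds. Section 11.8 conditions on no effect where a futility rule needs an assumed effect, and at t = 0.5 it recommends continuing only if interim z exceeds 1.93. The size of the harm depends on the true effect. If the recommendation is followed, the 80% power target is missed throughout the grid for 17 vs 16 and in many cells for 17 vs 15.5, while it mostly survives for 17 vs 15. An information fraction below one half would make the rule stricter.

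These figures assume the usual Brownian-motion approximation for the test statistic, the correlations and variance model of section 11.2, and a board that follows the recommendation. The one-sided null in section 11.8 against two-sided testing in section 11.5.1 is a smaller inconsistency that should be settled in the same edit.

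**What to change.** Rewrite the rule in section 11.8:

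- Compute P(.) under a stated design alternative instead of B1 = 0, and recommend stopping only if that conditional power is below 20%.
- Choose the alternative so that the interim can still stop when there is no effect, and report the stopping rates under no effect and under the design effect. With alternative drift θA the bound is z = (1.960 − θA(1−t) − 0.8416√(1−t))/√t. For the drift giving 80% power (θA = 2.80) at t = 0.5 this is (1.960 − 1.401 − 0.595)/0.7071, about −0.05. Stopping is then recommended 48% of the time under no effect and 2% under the design effect; net power is 79.7%, a loss of about 0.3 points.
- Do not simply take 17 vs 15 as the alternative. Its drift is about 3.9 to 7.1 over the grid, so at t = 0.5 the rule would recommend stopping only about 0.1–21% of the time under no effect, and the interim would do little.
- State that the rule is non-binding, define which effect B1 is at the interim, and use the information fraction that follows from it.
- Reconcile H0: B1 > 0 with the two-sided test of section 11.5.1.

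The cost is one paragraph in section 11.8 and a matching change in the monitoring board's charter. No participants are added.
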